The time taken to place the block will be recorded from the time the ultrasound probe is first placed on the child until completion of local anesthetic injection. The observer collecting postoperative data will not be present when the block is placed, and a band-aid will be placed over the supraclavicular fossa in all patients to maintain blinding of the observer to the group assignment. During the operation patients can receive intraoperative fentanyl, 1 mcg/kg IV at a time, if the attending anesthesiologist believes it is clinically indicated. At the end of the operation, anesthetic gases will be discontinued while the patient breathes 100% oxygen. The trachea will be extubated when the patient responds to commands, and the child will then be taken to the Post Anesthetic Care Unit (PACU) in keeping with standard practices. A validated pain scale (verbal rating scale where 0 = no pain and 10 = worst possible pain ever) will be used throughout to assess the severity of pain in the postoperative period. In keeping with current practice, patients with pain scores >4 will be treated with morphine 0.05mg/kg IV at 10 minute intervals until the score is below 4. Oral acetaminophen with hydrocodone (Lortab elixir 0.15mg/kg hydrocodone) will be administered to children for pain scores between 2-3. Supplemental oxygen, rescue antiemetic and antipruritic drugs will be administered in keeping with standard practices of TCH and the clinical judgment of the Attending Anesthesiologist. The duration of supplemental oxygen therapy, any medication administered and complications (side effects such as nausea, vomiting, itching, respiratory depression, prolonged awakening) will be recorded on the case report form.

The blinded observer will record pain scores within 15 minutes of arrival in the PACU and at 30 minutes, 1,2,6,12,24, and 48 hours after arrival in the PACU. If the child is sleeping at this time, the scores will be recorded when awake. The observer will also document any additional medication, the dose and the time given.

Prior to discharge home, parents will be educated on use of the 0-10 pain scale and given a diary to keep an accurate record of postoperative pain issues through the study period. The goal is to capture maximum pain scores at rest and with movement. Patient and parental satisfaction with pain management and with the global perioperative experience will also be graded on a numeric scale 0-10 scale.

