Time to readiness for discharge will also be measured from the time the patient enters the PACU to when the patient attains an Aldrete score of 9-10. This is a standardized scale used to assess discharge readiness at TCH and is listed below:

Aldrete Scoring System Activity Can move voluntarily or on command 4 extremities 2 2 extremities 1 0 extremities 0  
 Respiration Can deep-breathe and cough freely 2 Dyspnea, shallow or limited breathing 1 Apneic 0 Circulation  
 Preoperative BP (mmHg) BP  $\pm$  20 mmHg of baseline 2 BP  $\pm$  20-50 mmHg of baseline 1 BP  $\pm$  20 mmHg 0 Consciousness  
 Fully Awake 2 Arousalable on calling 1 Not responding 0 Color Normal 2 Pale, dusky, blotchy 1 Cyanotic 0 Score of 10: ready for discharge

If the patient is discharged before the end of a 48 hour period after surgery, they will be given a diary to complete to list all medications given, and to assess their pain at various time intervals (12,24, 48 hours after surgery), along with their satisfaction with pain control. The patient will be contacted after discharge to obtain the data in the diary. Phone calls will also be placed on POD #1,2, & 3 to the family following to assess measured endpoints (pain, medication usage, satisfaction, resolution of nerve block). We will examine the differences in subjects who did or did not return the diaries regarding group assignments, age, gender, ASA physical status, duration of surgery, intraoperative opioids medications, time of the PACU stay, mean and peak pain scores and recorded opioid consumption in the PACU before discharge.

At the time of their follow up visit to the surgeon, a complete physical examination will be done including a neurological evaluation for any nerve injury.

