## G2. Data Analysis

Provide a description of your plan for data analysis. State the types of comparisons you plan (e.g. comparison of means, comparison of proportions, regressions, analysis of variance). Which is the PRIMARY comparison/analysis? How will the analyses proposed relate to the primary purposes of your study?

The primary endpoint of the study will be the peak or maximum pain score in the postoperative period. The secondary endpoints in the study will include (1) Opioid consumption in morphine equivalents (2) Time to first analgesia request (3) Time to achieving discharge readiness (4) Incidence of side effects such as vomiting, respiratory depression, itching, dysphoria, compartment syndrome (5) Patient and parental satisfaction. In order to keep the statistical analysis robust, we will also examine the differences in subjects who did or did not return the diaries regarding: a. group assignments b. age c. gender d. ASA physical status e. duration of surgery f. intraoperative opioids medications g. time of the PACU stay h. mean and peak pain scores and i. recorded opioid consumption in the PACU before discharge. These are known factors k that affect postoperative pain and failure to show a difference in these factors may suggest that the missing 48 hour data can be considered to be missing at random. We will also examine the PACU pain and opioid consumption data(first 2 hr after surgery) for all cases and separately for cases where the diaries were returned with the 48 hour data. If the conclusions regarding the secondary endpoints of pain in the PACU were not altered and the known factors affecting postoperative pain did not differ between those who did and did not return the diaries, it may suggest the conclusions are still robust. Our current plan will be modified to include not only daily phone calls from researchers, but Epic Mychart as well for protected email communication to better gather data.

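### The diary for discharged children omits the scheduled 6 hour pain score, so the times covered by the primary peak may depend on when a child goes home

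*Combined protocol and SAP*

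**What the plan says.** Section F2 (Procedure) of the combined protocol and SAP has the blinded observer record pain within 15 minutes of PACU arrival and then "at 30 minutes, 1,2,6,12,24, and 48 hours after arrival in the PACU". That is eight times, counted from PACU arrival.

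Later in F2, a second schedule covers children who leave early: "If the patient is discharged before the end of a 48 hour period after surgery, they will be given a diary to complete". The diary is to list medications and "to assess their pain at various time intervals (12,24, 48 hours after surgery". That is three times, counted from surgery, and 6 hours is not among them.

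Three other statements in F2 bear on the gap:
- Parents are "given a diary to keep an accurate record of postoperative pain issues through the study period"; no times are named.
- The aim of this record is stated: "The goal is to capture maximum pain scores at rest and with movement".
- "Phone calls will also be placed on POD #1,2, & 3 to the family", with pain among the items assessed; no recall window is given.

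G2 (Data Analysis) says: "The primary endpoint of the study will be the peak or maximum pain score in the postoperative period". It does not say which time points or sources form the peak, or whether rest or movement scores are used. G2 lists time to discharge readiness as a secondary endpoint. Section C notes that pain after these operations can hold up discharge.

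**The concern.** A maximum can only stay the same or rise as observations are added. If the peak is formed from scheduled scores, a child in hospital at 6 hours has one more chance to record a high value than a child already at home. Section C links pain to time of discharge, so the number of scores could depend on treatment and differ between arms. Part of a difference in peak pain could then come from the collection schedule.

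The gap also bears on the hypothesis in Section D, which concerns longer as well as better analgesia. The hours between leaving hospital and 12 hours contribute to that question, and for children who go home early they have no specified pain score.

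The planned missing-data check does not cover this. It compares families who did and did not return the diary, and it refers to missing 48 hour data. A diary that is fully completed and returned still has no 6 hour entry.

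**Working it through.** **1. The two schedules side by side (F2).**

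| Time | Observer (from PACU arrival) | Diary (from surgery) |
|---|---|---|
| within 15 min | yes | no |
| 30 min | yes | no |
| 1 h | yes | no |
| 2 h | yes | no |
| 6 h | yes | no |
| 12 h | yes | yes |
| 24 h | yes | yes |
| 48 h | yes | yes |

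Scheduled scores by time of going home:
- in hospital to 48 h: 8
- home after the 2 h score and before 6 h: 8 − 1 = 7 (6 h lost)
- home between 1 h and 2 h: 8 − 2 = 6 (2 h and 6 h lost)

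**2. The plan's own figure (G1).** With difference 2, SD 2.9, two-sided alpha 0.05 and 80% power, the normal formula is n = 2 × [2.9 × (1.960 + 0.842) / 2]² = 33.0 per group. It gives 33.005 before rounding, so 34. The exact t-test gives 33.99, also 34. The stated 34 is reproduced. At 40 per group the t-test power is 86%. A 6 hour entry changes none of these inputs.

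**3. Loss in the peak from one missing score.** All of the following are assumptions: eight normal scores with equal means, SD 2.9 at each time, a common within-child correlation ρ of 0.3 to 0.7, and discharge unrelated to the scores themselves. The expected maximum of k such scores exceeds the mean by SD × √(1 − ρ) × e(k). Here e(k) is the expected maximum of k independent standard normal values: e(8) = 1.4236 and e(7) = 1.3522, a difference of 0.0714.

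- ρ = 0.3: 2.9 × 0.837 × 0.0714 = 0.17
- ρ = 0.5: 2.9 × 0.707 × 0.0714 = 0.15
- ρ = 0.7: 2.9 × 0.548 × 0.0714 = 0.11

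A simulation with scores rounded and limited to 0–10, mean 2.8, gives the same range when pain is flat over time (0.11 to 0.17). If 6 hour pain is assumed to be 1 point higher than at other times, the loss is 0.29 to 0.32. If 2 points higher, it is 0.57 to 0.63.

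**4. From a child's loss to a difference between arms.** The spurious difference is the loss times the difference between arms in the proportion missing the 6 hour score. With flat pain and an assumed 30 percentage points, it is 0.30 × 0.11 to 0.30 × 0.17, about 0.03 to 0.05 points. Over 10 to 50 percentage points and all three pain profiles, the range is about 0.01 (0.10 × 0.11) to 0.32 (0.50 × 0.63).

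**5. Effect on the test when there is no true difference.** Put δ = spurious difference / [SD of peak × √(2/n)]. The two-sided error is Φ(δ − 1.96) + Φ(−δ − 1.96). The most adverse case has difference 0.286, simulated SD of the peak 2.08 and n = 40. It gives δ = 0.286 / (2.08 × 0.2236) = 0.615 and an error of 9.4%. Across all cases the range is 5.0% to 9.4% at 40 per group. G1 also enters a total of 188, or 94 per group; there the range is 5.0% to 15.6%. The upper ends need both a 2-point excess of pain at 6 hours and a 50-point difference between arms in the proportion missing the score.

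**The case against.** A reader might infer that pain between discharge and 12 hours cannot be collected at all. The documents do not support that. The diary instruction covers the whole study period, the stated goal is to capture maximum scores, and calls are planned on the first three postoperative days. Any of these could bring in a worst score from the gap. What remains is that none of them names 6 hours, sets a recall window, or says how a recalled score is combined with scheduled ones.

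A reader might also infer that the comparison is biased by treatment. This too goes further than the text:
- The secondary endpoint is readiness, defined in F2 by an Aldrete score of 9–10. It is not time of going home, and pain is not an Aldrete item.
- The documents give no times of going home, no predicted difference in them between arms, and no pain profile by hour.
- G2 does not define which scores form the peak, so a peak over unequal times is a possibility and not a stated rule.
- The SD of 2.9 in G1 describes peak PACU scores, yet the calculation uses it for each single score.

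All of this stands. Section C makes a link between pain and discharge possible, but gives neither size nor direction.

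Two smaller objections also hold. The claim of longer analgesia does not depend on the 6 hour score alone, because time to first analgesia, the medication record and the calls about block resolution contribute as well. The two time zeros should differ little against marks at 12 to 48 hours.

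**Conclusion.** The concern holds in a limited form. The two schedules in F2 do not agree: 6 hours is planned for every child but has no named entry for a child already at home. Because the primary endpoint is a maximum with no defined time points or sources, the set of times it covers may depend on time of discharge.

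The likely effect is small. With flat pain and a 30-point difference between arms in the proportion missing the score, the 0.03 to 0.05 point shift is 1.5% to 2.5% of the 2-point target (0.03/2 and 0.05/2). Even the largest assumed case, 0.32 points, is 16% of it (0.32/2). In this model any shift would favour the arm with more early discharges; the documents do not show which arm that would be, or that there is one. The point is worth correcting because the correction costs little and concerns data that cannot be recovered reliably later. It does not threaten the design.

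**What to change.** 1. Add a 6 hour row to the diary, and a 2 hour row for any child discharged before 2 hours. Ask for those scores on the first postoperative call.
2. Use PACU arrival as time zero in both schedules.
3. Record rest and movement scores separately at every time point.
4. In G2, define the primary peak by a fixed list of time points and sources and by one of the two scores (rest or movement), the same for every child. State whether a recalled worst score may enter it.
5. Add a sensitivity analysis of the peak restricted to times available for all children.

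The cost is one or two diary rows, a few lines of text and slightly more work for parents. The sample size of 34 (40 with dropouts) per group in the G1 justification is unaffected.

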## Section I: Potential Benefits

Describe potential benefit(s) to be gained by the individual subject as a result of participating in the planned work.

Patients in the nerve block group may benefit from participating in the study as they may need less additional pain medication after surgery and have fewer side effects from these drugs. If a patient is assigned to the IV group, there are no benefits besides those benefits the patient would experience regardless of participation in the study.

Describe potential benefit(s) to society of the planned work.

Data from this study can be used to determine if children with supracondylar fractures will benefit from regional anesthesia in addition to general anesthesia.

Do anticipated benefits outweigh potential risks? Discuss the risk-to-benefit ratio.

There are no additional risks or benefits in the IV group as this is standard of care. The possible benefits from regional blockade include less pain with less overall opioid usage and less side effects from these drugs. The additional risks of neuropathy, pneumothorax, or other complications are low, and estimated at 0.4%-3% (PBID- 17377115; 19282715). Brachial plexus regional anesthesia is commonly performed at our institution for children having upper extremity surgery. The benefits to society include greater knowledge of the benefits of regional anesthesia in this situation and increased use of this modality in future.

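### Opioid-type side effects have no stated window and no named post-discharge collection, so the side-effect comparison rests on the period up to discharge and could mislead in either direction

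*Combined protocol and SAP*

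**What the plan says.** G2 lists as secondary endpoint (4) "Incidence of side effects such as vomiting, respiratory depression, itching, dysphoria, compartment syndrome". No start or end time is given. The analysis text compares the number of patients with side effects by Fisher's exact test or a Yates-corrected chi-square test.

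In F2, the one sentence that collects these events says that "complications (side effects such as nausea, vomiting, itching, respiratory depression, prolonged awakening) will be recorded on the case report form". It closes the text on PACU care and states no end time.

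The scheduled assessments that run beyond the PACU are about other things:

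- **Observer:** "The blinded observer will record pain scores within 15 minutes of arrival in the PACU and at 30 minutes, 1,2,6,12,24, and 48 hours". F2 adds: "The observer will also document any additional medication, the dose and the time given".
- **Diary, if discharge comes before 48 hours:** "given a diary to complete to list all medications given, and to assess their pain at various time intervals (12,24, 48 hours after surgery"; satisfaction is also collected.
- **Calls on POD 1, 2 and 3:** "to assess measured endpoints (pain, medication usage, satisfaction, resolution of nerve block".
- **Surgeon's follow-up visit:** a physical examination with a neurological evaluation for nerve injury; no date is given.

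G2 also adds MyChart messaging, without naming items. Section I says of children in the block group that "they may need less additional pain medication after surgery and have fewer side effects from these drugs".

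**The concern.** The plan follows the exposure (opioid use) at home but not the effects of that exposure. This would matter little if the timing of opioid use were the same in both arms, but the trial's hypothesis is that it is not. Section D expects more prolonged analgesia with the block, and G1 considers a 75% increase in time to first analgesia. Controls receive fentanyl after induction by allocation, and PACU morphine is triggered by pain score. If the hypothesis is right, control exposure may fall more heavily inside the observed period, and block exposure more heavily after it.

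The length of the observed period may also differ by arm, because time to discharge readiness is itself an endpoint.

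At stake is the reading of endpoint (4). A block that only postponed opioid use, with the same side effects over 48 hours, could appear to reduce them. In other circumstances a real reduction could be understated.

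**Working it through.** **1. Plan's own figures.** The documents give no figure for side effects by arm or by period. The only rate is in H1: postoperative nausea and vomiting in up to 40% of children. The one fully specified calculation, 34 per group for a difference of 2 with SD 2.9, reproduces (t-test solution 33.99, rounded up to 34), but it concerns pain scores. Two sample sizes are used below because G1 gives both 40 per group and 188 in total (188 / 2 = 94 per arm at 1:1). That mismatch is a separate matter.

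**2. What each instrument collects after discharge.**

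| Instrument | Pain | Medication | Satisfaction | Opioid-type side effects |
|---|---|---|---|---|
| Diary | yes | yes | yes | not named |
| POD 1–3 calls | yes | yes | yes | not named |
| Surgeon's visit | – | – | – | not named (physical and neurological examination) |

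**3. Illustration A: equal true incidence.** All inputs are assumptions. Recorded incidence = true 48-hour incidence × share of events before discharge. The last two columns give the probability that Fisher's exact p < 0.05, by exact enumeration over two binomials. True incidence is 30% in both arms.

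| Share before discharge, control / block | Recorded, control / block | 40 per arm | 94 per arm |
|---|---|---|---|
| 70% / 30% | 0.30 × 0.70 = 21% / 0.30 × 0.30 = 9% | 23% | 57% |
| 70% / 50% | 21% / 0.30 × 0.50 = 15% | 7% | 14% |
| 70% / 70% | 21% / 21% | 2.8% | 3.4% |

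The last row is the test's ordinary false-positive rate. With the 70% / 30% split, a true incidence of 20% gives 14% against 6% (11% and 36% of trials significant). At 40% it gives 28% against 12% (35% and 75%).

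**4. Illustration B: direction.** Let p be the risk before discharge and h the risk of a first event after discharge, so 48-hour incidence = 1 − (1 − p)(1 − h). Tilt toward the block is the 48-hour difference (block minus control) less the recorded difference:

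tilt = (1 − p_block) × h_block − (1 − p_control) × h_control

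Take p = 40% in control and 20% with the block (assumed, apart from the 40% anchor). The recorded difference is −20 points.

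| h control / h block | Tilt | 48-hour difference |
|---|---|---|
| 15% / 15% | 0.8 × 0.15 − 0.6 × 0.15 = +3 points | −17 |
| 15% / 30% | 0.8 × 0.30 − 0.6 × 0.15 = +15 | −5 |
| 10% / 30% | 0.8 × 0.30 − 0.6 × 0.10 = +18 | −2 |
| 20% / 10% | 0.8 × 0.10 − 0.6 × 0.20 = −4 | −24 |
| 30% / 15% | 0.8 × 0.15 − 0.6 × 0.30 = −6 | −26 |

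The tilt is zero at h_block / h_control = 0.6 / 0.8 = 0.75. Above that ratio, stopping at discharge favours the block; below it, stopping works against the block. With p = 40% in both arms the tilt is 0.6 × (h_block − h_control): +9 points for 15% / 30%, zero for equal home risks, and −9 points for 30% / 15%.

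**The case against.** **The collection gap may be smaller than it looks.** The case report form sentence has no explicit cut-off. The surgeon's examination covers nerve injury and might reveal the consequences of compartment syndrome, which is part of endpoint (4). Home antiemetic or antipruritic use would appear in the diary's medication list. The form, diary, call script and the data and safety monitoring attachment required by H2 are not in the text provided and may say more. This stands as a limit: the point is that the text names no post-discharge item for nausea, vomiting, itching or dysphoria, not that nothing is collected after discharge. The calls are described as covering measured endpoints, but the four items then listed leave side effects out.

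**The direction is not documented.** A reader might infer that the comparison is biased toward the block. The documents do not support that. They give no block duration, discharge time or home opioid use by arm. Discharge before 48 hours is conditional, so some deferred use may fall within the hospital stay. Control children may also take opioids at home. The control group's retrospective peak PACU score averaged 2.8, below the score above 4 that triggers IV morphine, so heavy PACU opioid exposure in controls is not established. H1 lists nausea and vomiting under general anesthesia, which both arms receive, and postponing opioids would not move those events home. Part of any early difference could be a real effect of the block strategy. All of this stands.

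**Impact is limited.** This is one of five secondary endpoints, no power is claimed for it, and the primary endpoint is untouched. Section I is a cautious benefit statement, not a trial claim. That bears on priority; the gap remains.

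**Conclusion.** The concern holds in a conditional form. Endpoint (4) has no window, and no diary, call or scheduled observer item in the text collects opioid-type side effects after discharge, while medication use is followed to 48 hours or POD 3. The comparison therefore rests in practice on the period up to discharge, and the recorded difference need not equal the 48-hour difference.

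The size cannot be taken from the documents. In Illustration A the spurious difference runs from zero (equal shares) through 6 points (21 − 15) to 12 points (21 − 9). In Illustration B the shift runs from 18 points toward the block to 9 points against it. Everything depends on how events divide around discharge in each arm, and the planned data cannot show that. The 23% and 57% figures belong to one assumed split and should not be quoted without the rest of the range.

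This is a cheap and worthwhile improvement to a secondary endpoint; it does not threaten the primary result.

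**What to change.** 1. Add identical yes/no items for nausea, vomiting, itching and dysphoria to the existing diary and the POD 1–3 calls, with the same prompts in both arms.
2. Define endpoint (4) as any occurrence from PACU arrival to 48 hours, and use one list of events throughout. Dysphoria is now named in G2 but not in the F2 recording sentence, and nausea the reverse.
3. Report in-hospital and post-discharge incidence separately by arm, and state that the in-hospital figure does not capture later opioid exposure.

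The cost is a few lines in instruments already in use and a short amendment. The downside is that home items are parent-reported and some will be missing. The comparison of children with and without returned diaries, already planned in G2, can be applied to them. Events not asked about at the time cannot be reliably recovered later.
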